5.3.2. Analysis Methods

Descriptive statistics and frequency tabulations will be used to present the parameters of long-term impact of RSV and its treatment with lumicitabine or placebo by previous treatment group at each analysis visit. For parameters that have continuous results (where the result is based on a scale from 0 to 10) descriptive statistics will be used, for the parameters with categorical results frequency tabulation will be used. The results will be presented graphically over time (mean for continuous parameters, stacked bar charts for categorical parameters).

Clinical diagnosis of eczema and allergic rhinitis within the first 2 years after the RSV infection per treatment group will be presented together with the 95% (2-sided) Wilson confidence intervals.

Listings will be provided for the parameters of long-term impact of RSV and its treatment with lumicitabine or placebo for each subject. Listings will also be provided for the clinical diagnosis of eczema and allergic rhinitis within the first 2 years after the RSV infection for each subject.

6. SAFETY

6.1. Reportable Adverse Events

6.1.1. Definitions

A reportable AE was defined in the protocol as a respiratory illness AE and/or an AE considered at least possibly related to study drug that was administered in study 64041575RSV2004 (lumicitabine or placebo), or a serious AE (SAE).

Information on eczema and allergic rhinitis was also asked to be collected in the questionnaire and has been collected as AEs. These will also be presented as reportable AEs. AEs that were reported but do not seem to fit the definition will be reported as *other*.

Reportable AEs will be categorized as:

- respiratory illness AE
- eczema
- allergic rhinitis
- other

The verbatim terms used in the eCRF by investigators to identify adverse events will be coded using the Medical Dictionary for Regulatory Activities (MedDRA). Events are looked at on the level of their preferred term.

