### **Secondary Endpoints**

The secondary endpoints during the follow-up period are:

- Percentage of wheezing days per month after the RSV infection, based on information reported by the parent/caregiver.
- Number of wheezing episodes after the RSV infection, based on information reported by the parent/caregiver.
- Incidence of reportable AEs and SAEs among subjects, based on information reported by the parent/caregiver and judged by the investigator. Reportable AEs include AEs related to respiratory illnesses and AEs considered at least possibly related to lumicitabine or placebo by the investigator.
- Number and type of respiratory infections among subjects, based on information reported by the parent/caregiver.
- Medical resource utilization including the number of medical visits, emergency room visits, and hospitalizations, all for respiratory conditions only, based on information reported by the parent/caregiver.

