### **9.4. Safety Evaluations**

Any SAEs or reportable AEs occurring during the study must be recorded on the AE section of the eCRF.

The following AEs will be considered reportable (within the context of this study):

- Respiratory illness AEs, including subsequent RSV infections.
- AEs considered at least possibly related to lumicitabine or placebo.
- SAEs (defined in Section 12.1.1).

The study will include the following evaluations of safety and tolerability according to the time points provided in the [Time and Events Schedule](#).

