#### **12.1. Definitions**

##### **12.1.1. Adverse Event Definitions and Classifications**

###### **Adverse Event**

An AE is any untoward medical occurrence in a clinical study subject administered a medicinal (investigational or non-investigational) product. An AE does not necessarily have a causal relationship with the treatment. An AE can therefore be any unfavorable and unintended sign (including an abnormal finding), symptom, or disease temporally associated with the use of a medicinal (investigational or non-investigational) product, whether or not related to that medicinal (investigational or non-investigational) product. (Definition per International Council for Harmonisation of Technical Requirements for Pharmaceuticals for Human Use [ICH]).

This includes any occurrence that is new in onset or aggravated in severity or frequency from the baseline condition.

Note: The sponsor collects AEs starting with the signing of the ICF to the last study-related activity. In this study, only reportable AEs (respiratory illness AEs and AEs considered at least possibly related to lumicitabine or placebo) and SAEs will be recorded.

Any AEs reported in Study 64041575RSV2004 ongoing at the entry visit of this LTFU study will be considered part of the subject's medical history. If the AE worsens during this study and is a reportable AE or SAE, it will be reported as also occurring in the LTFU study.

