Incidence of reportable AEs and SAEs, including AEs related to respiratory illnesses and AEs considered at least possibly related to lumicitabine or placebo by the investigator.	These incidences are defined as the number of AEs overall and by category divided by the 2 year reporting period. Each AE is counted as reported. The unit will be ‘per month/during the first 2 years’. In case the subject did not report on the full 24 months the divisor will be adapted to nearest number of months participating.
Number of respiratory infections per subject during study participation	The total number of respiratory infections of each subject. The unit will be ‘during study participation’. The respiratory infection AE terms (AEDECOD) will be determined based on medical review and reported overall and by Preferred Term.
Medical resource utilization including the number of medical visits, emergency room visits, and hospitalizations, all for respiratory conditions only, based on information reported by the parent/caregiver.	Total number of medical visits, emergency room visits, and hospitalizations, as reported by the parent/caregiver. The number will be given overall and by relationship to respiratory conditions, as based on medical review.

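### Pooled 'reportable AE' summaries in the SAP count eczema, allergic rhinitis and off-definition events, so they do not measure the protocol's closed set

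*SAP*

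**What the plan says.** Protocol 2.1.2 makes this a secondary endpoint: "Incidence of reportable AEs and SAEs among subjects, based on information reported by the parent/caregiver and judged by the investigator". It continues: "Reportable AEs include AEs related to respiratory illnesses and AEs considered at least possibly related to lumicitabine or placebo by the investigator". Protocol 9.4 lists three reportable types: respiratory illness AEs (including later RSV infections), AEs at least possibly related to lumicitabine or placebo, and SAEs. Protocol 12.1.1 closes the list: "In this study, only reportable AEs (respiratory illness AEs and AEs considered at least possibly related to lumicitabine or placebo) and SAEs will be recorded". Eczema and allergic rhinitis enter the protocol as questionnaire diagnoses (9.1.2, 9.1.3 and Attachment 2, Sections C and D), not as reportable AEs in their own right.

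SAP 6.1.1 repeats the protocol definition correctly. It then notes that eczema and allergic rhinitis were asked about in the questionnaire and collected as AEs, and states "These will also be presented as reportable AEs". Next it states "AEs that were reported but do not seem to fit the definition will be reported as" 'other'. It lists four categories of reportable AE: respiratory illness, eczema, allergic rhinitis and other.

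SAP 6.1.2 counts children with any reportable AE, with each category, with an SAE, by toxicity grade, and with events at least possibly related to the earlier study drug. For the secondary endpoint, SAP Table 2 (5.2.1) says: "These incidences are defined as the number of AEs overall and by category divided by the 2 year reporting period".

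**The concern.** The SAP classes as reportable some events that, in its own words, do not seem to meet the definition. A pooled figure labelled as reportable AEs would then describe a wider set than the endpoint of that name in the protocol.

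How the added events were found also matters. Protocol section 12 prefers open-ended, nonleading questions for AEs. Eczema and allergic rhinitis are instead asked about by name at each visit and monthly call until a diagnosis is reported. Off-definition 'other' events should not have been recorded at all under Protocol 12.1.1, so whether they are present depends on what a site chose to enter. A pooled figure that includes both groups partly reflects how the events were ascertained, not only the outcome the protocol names. In so small a study, a few such events could dominate the figure.

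**Working it through.** The plan states no figure that depends on this definition. The check is a comparison of definitions, followed by simple arithmetic on the number enrolled.

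**1. Is the protocol set closed?** The verb in Protocol 2.1.2 could be read as non-exhaustive. Protocol 9.4 gives a three-item list, and the word 'only' in Protocol 12.1.1 settles it.

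**2. Which events does each document count?**

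| Event | Protocol set | SAP 6.1.1 category |
|---|---|---|
| Respiratory illness AE | in | respiratory illness |
| Related or serious, non-respiratory (not eczema or allergic rhinitis) | in | other |
| Eczema, neither related nor serious | out | eczema |
| Eczema, related or serious | in | eczema |
| Allergic rhinitis, neither related nor serious | not stated; depends on whether it is a respiratory illness | allergic rhinitis |
| Any other AE, neither related nor serious | out | other |

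So 'other' and eczema each hold both qualifying and non-qualifying events. Dropping whole categories would not recover the protocol set.

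**3. Which summaries are affected?** The 'any reportable AE' row and the toxicity-grade row in SAP 6.1.2 are affected. So is the overall rate in Table 2, if its overall count uses the 6.1.1 set. That is the natural reading, but Table 2 does not cite 6.1.1.

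**4. Do other planned rows give the protocol-defined total?** Let R, S and P be the children with a respiratory illness, serious or related event. The protocol total is

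|R ∪ S ∪ P| = |R| + |S| + |P| − |R∩S| − |R∩P| − |S∩P| + |R∩S∩P|.

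SAP 6.1.2 gives |R|, |S|, |P| and a row for events that are both serious and related. It gives no overlap with respiratory illness. SAP 5.2.2 cross-classifies respiratory infections by seriousness and relatedness, but infections are not all respiratory illness. From |R|, |S| and |P| alone, the total lies between the largest of the three and their sum, capped at 7. With assumed counts of 3, 1 and 1, that is 3 to 5 of 7 children, or 42.9% to 71.4%.

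**5. Size.** Input: 7 children (SAP 2.4). The arm split is not given.

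- Overall: one child whose only event is non-qualifying adds 1/7 = 14.3 points.
- Within an arm, for assumed splits: 6:1 gives 16.7 or 100 points, 5:2 gives 20 or 50, and 4:3 gives 25 or 33.3.
- Assumed illustration: 3 of 7 children with a protocol-defined event is 42.9%. One, two or three further children with only non-qualifying events give 57.1%, 71.4% or 85.7%.
- Table 2 scale, assumed counts for one child over 24 months: 3/24 = 0.125 per month with qualifying events only; 4/24 = 0.167 with one extra event; 6/24 = 0.250 with three.

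**The case against.** The strongest reply is that little of the safety analysis is touched. Protocol 11.5 asks for the percentage of children with each event, not a pooled total. SAP 6.1.2 delivers that by system organ class and preferred term, where added eczema or 'other' rows leave every other row unchanged. The three protocol criteria each have their own row. The SAP explains the addition openly and shows the added groups separately. There is no testing (SAP 1.3), the project was stopped (SAP 3), and with 7 children a reader could count the protocol set by hand from the listings. All of this stands, and it limits the point to the pooled figures.

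A reader might infer more, and the documents do not support it:

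- **That the whole safety endpoint is replaced.** The component rows, the preferred-term tables and the listings still follow the protocol.
- **That a related or serious haematologic event, the type described in Protocol 1.1, would be hidden.** It falls under 'other' only in the category split. It would also appear in the serious or related row, by preferred term, by grade and in the listings.
- **That the added events exist only because sites over-reported.** This can apply to 'other' alone. The protocol's questionnaire asked for eczema and allergic rhinitis.
- **That allergic rhinitis is plainly outside the definition.** Attachment 2 defines it as an inflammation of the nasal passages, and the protocol does not limit respiratory illness to the lower tract. Eczema and 'other' are the clear departures.

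The reply does not show that the pooled figures match the definition whose name they carry, or that any planned summary row does.

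**Conclusion.** The point holds for the pooled summaries only. The 'any reportable AE' row, the toxicity-grade row and, on the natural reading, the Table 2 overall rate count events outside the protocol's closed set, and no planned summary row gives the protocol-defined total. One reclassified child shifts the overall proportion by 14.3 points. That is a possible shift and not an observed one, because the documents give no AE counts, and the within-arm figures rest on assumed splits. The consequence is descriptive: no test, interval or decision in the plan depends on it. It should be corrected because the label and the content disagree and the correction is cheap, but it does not undermine the rest of the safety reporting.

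**What to change.** In SAP 6.1.1, 6.1.2 and Table 2:

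- Flag each AE, whatever its category, as meeting the protocol definition (respiratory illness, at least possibly related, or serious) or not. Have medical review state whether allergic rhinitis counts as a respiratory illness.
- Report the 'any reportable AE' row, the toxicity-grade row and the Table 2 overall rate on flagged events only.
- Show non-qualifying eczema, allergic rhinitis and other AEs in separate rows as additionally collected events.
- Split 'other' into qualifying and non-qualifying.

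The flag should work event by event. Excluding all eczema and allergic rhinitis would drop any case that is serious, related or judged a respiratory illness, which would be a new departure from the protocol.

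The cost is some SAP wording and one derived variable. Relationship to the earlier study drug is already recorded in the eCRF (Protocol 12.2.1), and SAP 6.1.2 already reports by seriousness and respiratory illness, so no new data are needed. The 'any reportable AE' figure may become smaller. No event is lost: all stay in the listings, and eczema and allergic rhinitis keep their own exploratory summaries (SAP 5.3).

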6.1.2. Analysis Methods

A summary by treatment and overall of number of subjects with at least one event will be provided for the following reportable adverse events:

- any reportable adverse events,
- respiratory illness,
- eczema,
- allergic rhinitis,
- other,
- serious adverse events,
- reportable adverse events by toxicity grade,
- reportable AEs at least possibly related to study medication administered in study 64041575RSV2004,
- serious reportable adverse events that were at least possibly related to study medication administered in study 64041575RSV2004.

Tabulations will be reported by treatment and overall by category for the number of events experienced by a subject. A tabulation by system organ class and preferred term will be generated.

Listings will be provided for at least the following categories: all reportable AEs, serious AEs, reportable AEs leading to death, grade 3-4 reportable AEs, complications related to the RSV experienced during study 64041575RSV2004 (sorted by type of complication).

7. MEDICAL RESOURCE UTILIZATION

7.1. Definition

The following parameter will be considered:

Table 4: Calculations and Conversion Formulae (Medical Resource Utilization)

Measurement	Formula
Medical encounters: number of medical visits	The number of medical encounters due to respiratory conditions for each visit, derived from the eCRF overall and by type of medical encounter (as recorded). Counted as the number of unique medical encounters per subjects based on the unique combinations of the medical encounter start date and type of medical encounter.
Medical encounters: number of emergency room visits	The number of emergency room visits due to respiratory conditions for each visit, derived from the eCRF when type of medical encounter equals to emergency room.
Medical encounters: number of hospitalizations	The number of hospitalizations due to respiratory conditions for each visit, derived from the eCRF when type of medical encounter equals to hospital inpatient department, intensive care unit or Hospice/Palliative Care Unit.

7.2. Analysis Methods

Frequency tabulation will be used to summarize the number of medical encounters by categories and type of medical encounters per month by previous treatment group. A listing will be provided for the medical encounter records of each subject.

REFERENCES

1. Clinical Trial Protocol 64041575RSV2004, “A Phase 2, Randomized, Double-blind, Placebo-controlled Study to Evaluate the Antiviral Activity, Clinical Outcomes, Safety, Tolerability, and Pharmacokinetics of Orally Administered Lumicitabine (JNJ-64041575) Regimens in Hospitalized Infants and Children Aged 28 Days to 36 Months Infected with Respiratory Syncytial Virus”.
2. Clinical Trial Protocol 64041575RSV2002, “A Long-term Follow-up of Study 64041575RSV2004 to Evaluate the Impact of Lumicitabine (JNJ-64041575) on the Incidence of Asthma and/or Wheezing in Infants and Children with a History of Respiratory Syncytial Virus Infection”.
